10.2.1. Tabulation of Adverse Event Data

The following tables will be produced to summarize AE data. For the following tables, subjects will be counted only once at each level of summarization.

• An overall summary of the number and percentage of subjects reporting TEAEs, TEAE severity, serious TEAEs, treatment-related TEAEs, related serious TEAs, TEAEs leading to interruption of study drug, TEAEs leading to permanent withdrawal of study drug; related TEAEs leading t

Summary tables by treatment group of the number of subjects (and percentage) with TEAEs as follows:

- TEAEs overall and by system organ class and preferred term
- Most common TEAEs (>=5% in any treatment group) by preferred term
- TEAEs by maximum severity, overall and by system organ class and preferred term
- Treatment-related TEAEs overall and by system organ class and preferred term
- Serious TEAEs, overall and by system organ class and preferred term
- Serious, treatment-related TEAEs overall and by system organ class and preferred term

• TEAEs leading to permanent withdrawal of study medication, overall and by system organ class and preferred term

Additional TEAE summaries will be provided by treatment group, including the number and percentage of subjects experiencing TEAEs for the following:

- TEAEs overall and by SOC and PT, including the following subgroup analyses:
 - Asthma comorbidity

These summaries will be prepared for TEAEs occurring during the treatment period. Similar summaries as above will be provided for AEs starting during the Safety Follow-up Period with the exception of AEs leading to permanent withdrawal of study medication and the subgroup analyses, which will be provided for the TEAEs only. Denominators for the Safety Follow-Up Period AE summaries will be based on the number of subjects entering the Safety Follow-Up Period.

In addition to the listing of all AEs, separate listings will be provided of serious AEs, AEs leading to permanent withdrawal of study medication, and AEs leading to death. TEAEs will be identified on each listing.

10.3. Laboratory Evaluations

Laboratory safety parameters will be analyzed by a central laboratory using standard validated methods. All laboratory safety data will be collected as per the schedule of assessments given in Table 1.

The following laboratory parameters will be collected:

- Hematology: hemoglobin, hematocrit, mean cell hemoglobin, mean cell volume, mean cell hemoglobin concentration, platelet count, red blood cell count, white blood cell with differential (neutrophils, lymphocytes, monocytes, eosinophils, basophils)
- Blood Biochemistry: alanine aminotransferase (ALT; SGPT), albumin (ALB), alkaline phosphatase (AP), aspartate aminotransferase (AST; SGOT), bicarbonate, bilirubin (total), bilirubin (direct), blood urea nitrogen (BUN), calcium (Ca), chloride (Cl), creatinine, creatine kinase, C-reactive protein, gamma-glutamyl transferase (GGT), glucose, lactate dehydrogenase (LDH), phosphate (inorganic), potassium (K), sodium (Na), total cholesterol (?fractions), total protein, triglycerides, troponin-I, uric acid.
- Urinalysis: bilirubin, blood (occult), glucose, ketones, leukocytes esterase, nitrites, pH, protein, specific gravity, urobilinogen.
- Follicle stimulating hormone: Luteinizing Hormone (LH), Follicle Stimulating Hormone (FSH)
- Immunoglobulin: Immunoglobulin E
- Viral Serology: hepatitis B surface antigen, hepatitis B and C antibody, HIV 1 and 2 antibodies
- Pregnancy tests: serum pregnancy test (human chronic gonadotropin), urine pregnancy dipstick
- Urine drug screens: amphetamine; barbiturates; benzodiazepines; cocaine; ethanol; marijuana; 3,4-Methylenedioxymethamphetamine (MDMA; ecstasy); methadone; methamphetamine; opiate; oxycodone; phencyclidine; TCA

• Tuberculosis B (TB) test: purified protein derivative (PPD) skin test, QuantiFERON® TB Gold (QFT)

Laboratory results collected in conventional units will be converted to International System of Units (SI) for all summaries and listings.

Observed continuous laboratory data will be descriptively summarized by type of laboratory test/parameter by treatment group. Changes from baseline will also be presented for all continuous laboratory parameters by treatment group over time. Shift tables using categories of low, normal, and high, comparing laboratory test results from Baseline to each visit will be presented with percentages based on subjects with a non-missing value at Baseline and post-baseline visit.

All laboratory values (including values, reference ranges, and possible flags (low, high)) will be presented in the subject data listings

Line plots for neutrophils and leukocytes will be produced by plotting actual values against the sample collection time point for individual subjects.

10.4. Vital Signs

Vitals signs including weight are obtained according to the schedule in Table 1. Vital signs assessments should be performed before blood sampling and before injection of study medication at each study visit where administered. Blood pressure readings should be obtained after approximately 15 minutes of rest in a seated position. Vital signs captured include body temperature, respiration rate, sitting radial pulse rate, and sitting systolic and diastolic blood pressures.

Descriptive summaries of observed and change from Baseline values will be presented for each vital sign parameter by treatment group and visit for Safety Analysis Set. The following conversion factor will be used to convert any temperatures reported in degrees Fahrenheit to Celsius:

Temperature (in °C) = 5/9 (Temperature [in °F]-32).

All vital signs values will be presented in the subject data listings.

10.5. ECG

At the screening, Day 1, Week 16/EOT and Week 24/EOS/ET visits, a single, standard, supine 12-lead ECG will be obtained after a subject has rested quietly for at least 10 minutes, using equipment provided from the central reader. The ECG is to be repeated up to 2 times if the result is abnormal, as clinically appropriate. For the analysis, the last measurement for the same visit will be included in the summary. If multiple measurements have the same date and time, the one recorded in the CRF will be evaluated for the summary table. ECG data will be submitted and reviewed by the central reader. The ECG will also be reviewed by the Investigator or an authorized representative who is experienced in the evaluation of ECGs and assessed for clinical significance.

Descriptive summaries of observed and change from Baseline values will be presented for each quantitative ECG parameter by treatment group and visit, including HR, PR, QRS, QT, QTcF, and RR.

ECG shift tables will be presented providing the count of subjects with each type of finding (normal, abnormal -NCS, or abnormal -CS) at Baseline compared to each post-baseline visit by treatment group with percentages based on subjects with a non-missing value at the Baseline and post-baseline visit.

The QTc values based on Fridericia formula will be rounded to the integer and the values will be categorized into the following ranges: >450 for male or >470 for female; >500 for the post-baseline visits. Summaries of the number and percentage of subjects per visit and overall post-baseline visit will be provided for each of these ranges.

The changes in QTcF values will be categorized into the clinical concern ranges, which are specific to changes in QTcF: 30-60 and >60 msec. A summary of change in QTcF value will display the number and percentage of subjects with a change within each range per each visit. Subjects with missing baseline values will be excluded from this summary. All ECG parameters including the finding will be listed.

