8.2.4 VITAL SIGNS

Vital signs captured include body temperature, respiration rate, sitting radial pulse rate, and sitting systolic and diastolic BPs. Vitals should be collected before blood sampling and before injection of study drug at each visit where administered (see Section 1.3). Blood pressure is collected after 15 minutes of rest in a seated position.

8.2.5 12-LEAD ECG

A single, standard, supine 12-lead ECG will be obtained after a subject has rested quietly for at least 10 minutes, using equipment provided from the central reader. The ECG is to be repeated up to 2 times if the result is abnormal, as clinically appropriate. ECGs must be collected on the ECG machine provided by ERT. ECG data will be submitted and reviewed by the central reader. The ECG will also be reviewed by the investigator or an authorized representative who is experienced in the evaluation of ECGs and assessed for clinical significance.

Instructions and guidelines for collection (eg, equipment), transmission, and archiving of ECG data will be provided in the ECG Manual. A 12-lead ECG will be obtained using a validated ECG machine that automatically calculates the HR and measures pulse rate, QRS, QT, and QTc intervals.

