6.2. Key Definitions

6.2.1. Baseline

Unless otherwise specified, "baseline" is defined as the last observed value of the parameter of interest prior to the first intake of study medication (this includes unscheduled visits). Definitions of baseline for specific efficacy and/or safety parameters are provided in relevant sections where those parameters are defined and their analysis methods described.

For numerical variables, change from baseline will be calculated as the value of interest at the time of measurement minus the corresponding baseline value.

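### Only abnormal ECGs are repeated and only the last reading of a visit is tabulated, so the SAP's descriptive ECG tables can under-count abnormal and borderline-high QTcF readings

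*SAP*

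**What the plan says.** SAP 10.5 schedules ECGs at screening, Day 1, Week 16 and Week 24. At each visit "a single, standard, supine 12-lead ECG will be obtained after a subject has rested quietly for at least 10 minutes". Protocol 8.2.5 adds the repeat rule, which SAP 10.5 repeats: "The ECG is to be repeated up to 2 times if the result is abnormal, as clinically appropriate". The protocol does not say which reading is analysed. SAP 10.5 does: "For the analysis, the last measurement for the same visit will be included in the summary". A tie rule follows: "If multiple measurements have the same date and time, the one recorded in the CRF will be evaluated for the summary table".

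The outputs that draw on this selection are:

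- descriptive summaries of observed values and change from baseline;
- the shift table: "ECG shift tables will be presented providing the count of subjects with each type of finding" (normal, abnormal not clinically significant, abnormal clinically significant);
- QTcF categories (>450 ms for men, >470 ms for women, and >500 ms): "Summaries of the number and percentage of subjects per visit and overall post-baseline visit will be provided for each of these ranges";
- QTcF change categories (30-60 and >60 ms): "A summary of change in QTcF value will display the number and percentage of subjects with a change within each range per each visit".

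SAP 6.2.1 sets the general baseline, which "is defined as the last observed value of the parameter of interest prior to the first intake of study medication".

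**The concern.** A repeat is triggered by the result of the first tracing, and the repeat then displaces that tracing in the tables. Selection therefore depends on the outcome. A subject whose first tracing is abnormal can have up to two more chances to be recorded as normal. A subject whose first tracing is normal has no planned second chance to be recorded as abnormal.

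Changes in ECG parameters are a listed safety endpoint (Protocol Section 3, SAP 4.5). There are only two scheduled post-baseline ECGs and about 33 subjects per arm, so one or two displaced readings can change or empty a category cell. At stake is whether the ECG tables give a fair count of abnormal and borderline-prolonged readings.

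**Working it through.** **Step 1: look for another rule that governs repeats.** The SAP 6.1 rule (value closest to the target date) applies only unless otherwise specified, and SAP 10.5 specifies otherwise for ECGs. The tie rule covers only readings with the same date and time. Neither document gives a first-reading, worst-value, any-abnormal or replicate-mean rule for ECGs. SAP 10.5 therefore governs as written.

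**Step 2: direction, table by table.**

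- *Shift table.* The trigger is an abnormal result and the table counts abnormal results, so post-baseline abnormal totals can only be lowered by replacing an abnormal first tracing with a normal repeat. Individual cells can move either way, because baseline abnormal findings can be replaced too.
- *QTcF >450/>470.* Counts fall where a borderline-high QTcF prompts the repeat. No QTcF trigger is written down. If rhythm or morphology prompts the repeat, QTcF can move either way.
- *Change from baseline.* Uncertain. Baseline is the last pre-dose value, so the same filter can lower baseline and raise the change.
- *Overall post-baseline row.* Not stated. SAP 10.5 does not say whether a replaced reading counts.

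**Step 3: size.** The documents give no ECG variability, abnormality rate or repeat frequency, so there is no figure to reproduce. Everything below is assumed.

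Take a man with true QTcF μ and within-visit SD σ, with independent readings. Every reading above 450 ms is repeated until normal, at most twice, and rounding to whole milliseconds is ignored. Then

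p = 1 − Φ((450 − μ)/σ)

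The chance of being counted is p on the first reading, p² on the last reading if one repeat is allowed, and p³ if two are allowed, since every reading must then be abnormal. With σ = 10:

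| True QTcF | First reading, p | One repeat, p² | Up to two repeats, p³ |
|---|---|---|---|
| 445 ms | 0.309 (31%) | 10% | 0.029 (3%) |
| 455 ms | 0.691 (69%) | 48% | 0.331 (33%) |
| 465 ms | 0.933 (93%) | 87% | 0.813 (81%) |

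Sensitivity to σ at 455 ms, where p = Φ(5/σ):

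- σ = 5: 0.841, cubed 0.60
- σ = 8: 0.734, cubed 0.40
- σ = 15: 0.631, cubed 0.25

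**Step 4: per arm.** A simulation assumed a mean of 420 ms, between-subject SD 18, within-visit SD 8 and the >450 ms cut-off for everyone:

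| Rule | Rate >450 ms | Per 33 subjects |
|---|---|---|
| First reading | 6.1% | 2.0 |
| Last, one repeat | 3.4% | 1.1 |
| Last, up to two repeats | 2.5% | 0.8 |
| Share with true value >450 ms | 4.8% | 1.6 (33 × 0.048) |

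Across assumed means of 410-430 ms and within-visit SDs of 5-12, the share of first-reading outliers lost was 24%-66% with one repeat and 34%-82% with up to two. These are upper-end figures, because the text leaves repetition to clinical judgement.

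**The case against.** Repeating an abnormal ECG is ordinary practice, and the last tracing may be the technically better one. In the 445 ms row the subject is not truly above 450 ms, so the fall from 31% to 3% removes false positives and improves classification. That stands, and the 445 ms row should not be read as lost signal. It does not settle the matter. The SAP rule is not limited to technically poor tracings, and in the Step 4 example both last-reading rates fall below the true share of 4.8%. Some real prolongation is therefore dropped along with the noise.

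The loss also fades with distance from the cut-off. At a true 490 ms, σ = 10, virtually every reading exceeds 450 ms, all three are taken, and the last exceeds 500 ms with the same probability as the first: 1 − Φ(1) = 16%. Clear prolongation is not hidden by this route.

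Stronger readings that a reader might infer, and that the documents do not support:

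- *Abnormal readings disappear from safety reporting.* SAP 10.5 lists all ECG parameters and findings. Protocol 9.4.3.3 lists clinically significant abnormalities by subject. Protocol 8.6.1 requires a clinically significant post-injection change to be reported as an adverse event, so it also reaches the adverse event tables. Readings judged not significant remain in the listing only.
- *The overall post-baseline QTcF count is built from retained readings.* Its derivation is simply not given.
- *All ECG tables are biased the same way.* This fails for the change tables, and for QTcF when something else prompted the repeat.
- *The rule favours etokimab.* It is identical in all arms and applied under blinding.

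**Conclusion.** The point holds as one of record selection in descriptive safety tables. Followed as written, SAP 10.5 under-counts abnormal findings in the post-baseline columns of the shift table whenever a repeat turns out normal. It also under-counts QTcF >450/>470 where a borderline-high QTcF prompted the repeat. Any true difference between arms is diluted, with no arm favoured. The direction for change-from-baseline tables is uncertain, and the treatment of repeats in the overall post-baseline row needs to be stated.

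The size cannot be derived from the documents. Under the upper-end assumptions above, the loss is material just above the cut-off (33% against 69% at 455 ms), modest 10 ms higher (81% against 93% at 465 ms), and about one subject per arm in the worked example. No alpha, power or sample-size figure is affected. The change is worth making before unblinding because it is cheap and uses readings already collected.

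**What to change.** In SAP 10.5, replace the last-measurement rule with this: descriptive, change-from-baseline, shift and QTcF category tables use the first tracing at the visit that the central reader judges technically valid. Apply the same rule at baseline, as a stated exception to SAP 6.2.1, so that change from baseline compares like with like.

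Add a separate, labelled row counting subjects with any post-baseline tracing in each QTcF category, including repeats and unscheduled ECGs. Footnote it to say that subjects with repeats contribute more readings and that some values did not persist. State explicitly which rule the overall post-baseline row follows.

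The any-tracing count should not replace the main count, because it carries the opposite bias. At a true 490 ms, σ = 10, with three readings, the chance of being counted above 500 ms rises from 16% to 1 − 0.841³ = 40%.

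The cost is a short SAP revision, one derivation flag and one table row. Abnormal counts will be slightly higher, and some will be transient. How sites repeat ECGs is untouched.

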10.6. Physical Examination

A complete physical examination will include examination of the following parameters and body systems: skin, neck (including thyroid), head, eyes, ears, nose, throat, heart, lungs, abdomen, back, lymph nodes, extremities, vascular and neurological. If indicated based on medical history and/or symptoms, rectal, external genitalia, breast, and/or pelvic exams may be performed.

At screening, a complete physical examination will be performed. At baseline and post-treatment visits, the physical examination may be abbreviated, as deemed medically appropriate at the discretion of the investigator.

Significant physical examination findings which meet the definition of an adverse event will be recorded on the AE page post-treatment; significant findings that are present prior to investigational product administration are included on the Medical History page.

Physical examination results will be provided in a listing only.

10.7. Other Safety

10.7.1. Pregnancy Tests

Pregnancy test results will be provided in a listing only.

10.7.2. Immunogenicity Analysis

Blood samples will be taken for ADA analysis at pre-dose, week 4, 8, 12, 16, 20, and 24 (EOS).

A subject will be considered to be positive for etokimab-induced immunogenicity if one of the following criteria is met:

1. A missing pre-dose immunogenicity assessment and a confirmed positive immunogenicity response after dosing.

- 2. A negative pre-dose immunogenicity assessment and a confirmed positive immunogenicity response after dosing.
- 3. A positive pre-dose immunogenicity assessment and a confirmed positive immunogenicity response after dosing.

Observed values for ADA levels/status and the neutralizing antibody levels/status will be listed by subject and summarized with descriptive statistics based on the Safety Analysis Set. The frequency and percentage of confirmed positive immunogenicity response will be summarized by treatment groups. If data permits, correlation will be assessed between ADA levels and safety and efficacy endpoints.

Titer values will be summarized by treatment using mean and median. The frequency and percentage of patients with categorical result assessments will be summarized by treatment groups at each available visit and time point.

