8.5 IMMUNOGENICITY

Antibodies to etokimab will be evaluated in serum samples collected from all etokimab-dosed subjects according to the SoA (See Section 1.3). Additionally, serum samples should also be collected at the final visit from subjects who discontinued study treatment or were withdrawn from the study. These samples

will be tested by the Sponsor or Sponsor's designee. Each serum sample will be divided into 2 aliquots (1 each for immunogenicity testing and a back-up).

Serum samples will be tested in a multi-tiered approach. A validated screening assay for antibodies binding to etokimab will be initially used to assess serum samples. Samples that are determined putative positive in the screening assay will then be subjected to a confirmatory assay to demonstrate that antibodies are specific to etokimab. Samples that are identified as positive in the confirmatory assay will be further characterized in a validated titer assay and the titer of confirmed positive samples will be reported. Other analyses may be performed to verify the stability of antibodies to study treatment and/or to further characterize the immunogenicity of study treatment.

The detection and characterization of antibodies to etokimab will be performed using a validated assay method by or under the supervision of the sponsor. Only samples which are within the window of sample stability will be analyzed. The time points for ADA sample collection is given in Appendix C.

Samples that are confirmed positive for antibodies binding to etokimab with a titer greater than the minimum required dilution of the validated assay may be further characterized and/or evaluated for their ability to neutralize the activity of the study treatment using a validated cell based neutralizing antibody assay method.

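### The SAP's rule for etokimab-induced ADA amounts to any confirmed post-dose positive, so it overcounts whenever a pre-dose positive persists without a titer rise

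*SAP*

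**What the plan says.** SAP 10.7.2 introduces the classification with "A subject will be considered to be positive for etokimab-induced immunogenicity if one of the following criteria is met". Each of the three criteria asks for a confirmed post-dose positive, and they differ only in the pre-dose result. In criterion 1 that result is missing, and in criterion 2 it is negative. Criterion 3 reads "A positive pre-dose immunogenicity assessment and a confirmed positive immunogenicity response after dosing".

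The same section then states "The frequency and percentage of confirmed positive immunogenicity response will be summarized by treatment groups". On titers it says only "Titer values will be summarized by treatment using mean and median"; titers are not used to classify a subject. It also plans by-subject listings of ADA status and a by-visit summary of categorical results.

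On the data available, Protocol 8.5 says of samples that pass the confirmatory step that they "will be further characterized in a validated titer assay and the titer of confirmed positive samples will be reported". The schedules of activities in both documents place an immunogenicity sample before the first dose.

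**The concern.** An induced antibody is one that treatment brought about. The pre-dose sample exists to tell it apart from reactivity that was already there. Prior etokimab exposure is exclusion criterion 1, so in an eligible subject a pre-dose positive reflects pre-existing reactivity or assay background. Criterion 3 nevertheless counts that subject as induced, with no condition on the size of the post-dose response.

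The plan applies a stricter standard to adverse events. In Protocol 9.4.3.1 and SAP 10.2, a condition already present at baseline counts as treatment-emergent only if it worsens. Criterion 3 has no such requirement.

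Immunogenicity is a listed secondary safety endpoint. A count labelled as induced that contains unchanged pre-existing antibody would misstate how immunogenic the product is. The error can go only upward.

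**Working it through.** Neither document states an ADA rate, so there is no planned figure to reproduce. The check has a logical part, which needs no data, and a size part, which rests on assumed inputs.

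**Logic.** Cross the three pre-dose states with the two post-dose results.

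| Pre-dose | Confirmed positive after dosing | SAP flag | Any post-dose positive | Pre-dose negative or missing, then positive |
|---|---|---|---|---|
| Missing | No | 0 | 0 | 0 |
| Missing | Yes | 1 | 1 | 1 |
| Negative | No | 0 | 0 | 0 |
| Negative | Yes | 1 | 1 | 1 |
| Positive | No | 0 | 0 | 0 |
| Positive | Yes | 1 | 1 | 0 |

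The SAP flag matches any post-dose positive in all six cells, so the pre-dose result never changes the classification. It departs from a baseline-aware rule in one cell, positive before and after dosing. That cell mixes genuinely boosted subjects with unchanged ones.

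**Size.** Definitions:

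- q = share of etokimab subjects positive before dosing
- s = share of those still confirmed positive after dosing
- b = share of those with a real titer rise (b ≤ s)
- i = share newly positive among the remaining subjects (missing pre-dose treated as negative)

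Formulas:

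- SAP rate = q·s + (1 − q)·i
- Induced plus boosted rate = q·b + (1 − q)·i
- Excess = q(s − b)

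The excess does not depend on i. The only input from the documents is about 33 subjects per arm (Protocol 9.2), hence 2 × 33 = 66 on etokimab. Everything else is assumed. The extreme case is s = 1 and b = 0; i = 10% is for illustration.

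| q | SAP rate | Induced plus boosted | Excess (points) | Excess subjects of 66 |
|---|---|---|---|---|
| 0% | 10.0% | 10.0% | 0 | 0 |
| 2% | 11.8% | 9.8% | 2.0 | 0.02 × 66 = 1.3 |
| 5% | 14.5% | 9.5% | 5.0 | 0.05 × 66 = 3.3 |
| 10% | 19.0% | 9.0% | 10.0 | 0.10 × 66 = 6.6 |

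With s = 80% and b = 20%, the excess at q = 5% falls to 0.05 × (0.8 − 0.2) = 3.0 points (13.5% against 10.5%). One misclassified subject adds 1/33 = 3.0 points to a single arm.

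The chance of at least one pre-dose positive among 66 is 1 − (1 − q)^66, which is 74%, 97% and 99.9% at q = 2%, 5% and 10%.

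**The case against.** The strongest reply is that this is a labelling fault with limited reach. Much of that reply stands.

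- **Downstream summaries.** A reader might infer that the ADA-by-exposure and ADA-by-efficacy analyses carry the misclassification forward. The documents do not support that. The optional concentration split in SAP 9.3.2 uses confirmed ADA status, and the correlations in SAP 10.7.2 and Protocol 9.4.8 use ADA levels, if data permit. Neither is tied to the induced flag.
- **Pre-dose sample ignored altogether.** This too goes too far. The sample plays no part in the classification, but ADA status is listed by subject and summarized by visit, and SAP 6.4 Table 2d gives immunogenicity a baseline visit. Pre-dose positives can be found in the outputs, but nothing in the plan removes them from the induced count.
- **Which table carries the label.** The frequency summary refers to confirmed positive response, and the SAP's index of tables is not legible in the public text. A headline induced rate is therefore likely but not certain.
- **No placebo comparison.** Protocol 8.3 leaves placebo samples unassayed by default, which removes a background rate, but it allows them on request. Each etokimab subject's own pre-dose sample is in any case the more direct control.
- **Conservatism.** Overcounting a safety signal resembles the SAP's worst-case conventions for missing AE severity and relationship (SAP 6.3.4.2). Those conventions fill in missing data, however. Criterion 3 overrides a baseline result that was observed.

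The reply does not reach the rule itself: as written, it gives the wrong class to a subject with unchanged pre-existing antibody.

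**Conclusion.** The rule is wrong as written. The etokimab-induced flag is identical to any confirmed post-dose positive, and this follows from the text alone. The count will be overstated whenever a pre-dose positive persists without a titer rise, by q(s − b) relative to induced plus boosted.

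A reader might go further and conclude that induced immunogenicity is certain to be overstated, or that a given true rate would be reported at two or three times its value. The documents do not support either. They give no baseline rate, and the excess is zero if no subject is positive before dosing. The figure of about 3 to 7 of about 66 subjects is an upper bound for assumed q of 5–10%, with all persisting and none boosted.

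Criterion 3 also should not simply be deleted, because a pre-dose positive with a real rise is a legitimate boosted case.

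The consequence is confined to a descriptive secondary safety endpoint. The co-primary tests, alpha and power are unaffected.

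**What to change.** Replace the single flag in SAP 10.7.2 with these categories:

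- **Treatment-induced:** pre-dose negative, then confirmed positive.
- **Missing pre-dose, then confirmed positive:** shown on its own row, since it may also contain pre-existing antibody.
- **Treatment-boosted:** pre-dose confirmed positive, with a post-dose titer above the subject's own baseline by a prespecified factor. The factor should come from the assay validation; the documents contain nothing from which to choose it.
- **Pre-existing, not boosted:** reported separately and excluded from the induced count.

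Report pre-dose prevalence beside these. State also whether the pre-dose positive in criterion 3 means confirmed positive, because the present text says confirmed only for the post-dose result.

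If no factor can be justified, the minimum change is to relabel the present count as any post-dose confirmed ADA positive and break it down by pre-dose status.

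The cost is SAP wording and one derived variable, settled before the ADA results are unblinded. Pre-dose samples and titers of confirmed positives are already planned, so no new sample or assay is needed.
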